8. TRIAL OBJECTIVES

8.1. Primary Objective

- To evaluate the proportion of β -thalassemia patients who have an erythroid response, defined as: 1) a hemoglobin increase of ≥ 1.5 g/dL from baseline for ≥ 14 days (in the absence of red blood cell [RBC] transfusions) in non-transfusion dependent patients, or 2) $\geq 20\%$ reduction in RBC transfusion burden compared to pretreatment in transfusion dependent patients

8.2. Secondary Objectives

- To evaluate safety and tolerability of ACE-536
- To evaluate the proportion of transfusion dependent patients who have $\geq 50\%$ reduction of RBC transfusion burden compared to pretreatment
- To evaluate the time to erythroid response and duration of erythroid response
- To evaluate the change in hemoglobin level in non-transfusion dependent patients
- To evaluate the change in pre-transfusion hemoglobin levels in transfusion dependent patients
- To evaluate changes in biomarkers of erythropoiesis, hemolysis, iron metabolism, and bone metabolism
- To examine the pharmacokinetic (PK) profile of ACE-536 in patients with β -thalassemia

8.3. Exploratory Objective

- To evaluate biomarkers related to the TGF- β superfamily
- To evaluate self-reported quality of life using tools including but not limited to the FACT-An and SF-36 questionnaires (expansion cohort only)
- To evaluate change in spleen size by MRI
- To evaluate change in bone mineral density (BMD) by DXA
- To evaluate change in extramedullary hematopoiesis (EMH) mass size by MRI
- To evaluate change in leg ulcer size
- To evaluate change in the 6-minute walk test (6MWT) distance in NTD patients

9. OVERALL STUDY DESIGN AND PLAN: DESCRIPTION

This is a phase 2, open-label, ascending dose study to evaluate the effects of ACE-536 in patients with β -thalassemia.

9.1. Study Design

Patients who meet the study eligibility criteria will be enrolled within 28 days of screening. Patients in all cohorts will receive ACE-536, administered subcutaneously (SC), every 3 weeks for up to 5 cycles. ACE-536 cannot be administered after study day 85 (\pm 2 days). Dose delay(s) and dose reduction(s) may be required for individual patients as outlined in the Patient Dose Modification Rules ([Section 10.8.1](#)).

Each dose escalation cohort will consist of up to 6 patients. The dose level of ACE-536 for the first cohort will be 0.2 mg/kg and the dose level(s) for subsequent cohort(s) will follow a modified Fibonacci dose escalation scheme (i.e., maximum dose of 0.4 mg/kg for cohort 2, 0.6 mg/kg for cohort 3, 0.8 mg/kg for cohort 4, 1.0 mg/kg for cohort 5, etc.). Once a minimum of 3 patients in a cohort have completed Study Day 29, a Safety Review Team (SRT) will review preliminary safety and hematologic response data and make recommendations to the Sponsor regarding whether or not to enroll an additional cohort at a higher or lower dose, complete enrollment of 6 patients at the current dose level, or proceed to the expansion cohort.

The expansion cohort (n=30) will be treated with ACE-536 at a starting dose level not to exceed the maximum dose level for the previous cohorts. The expansion cohort will include a minimum of 12 patients who are non-transfusion dependent and a minimum of 12 patients who are transfusion dependent (including a minimum of 6 thalassemia major patients with onset of regular transfusions before age 4 years, and a minimum of 6 patients with onset of regular transfusions onset after age 4 years). For subsequent cycles in the expansion cohort, a patient's dose level may be titrated from the previous dose administered for that patient. Patients in the expansion cohort only may have their dose level titrated up or down as required per protocol to meet dose titration and modification rules (see [Section 10.8](#)). The maximum dose level given to a patient will not exceed the maximum dose level evaluated in the dose escalation cohorts. Patients will be treated with up to 5 doses of ACE-536.

Each TD patient in the expansion cohort will have a defined "pre-transfusion hemoglobin threshold" which will be calculated based on transfusion history and will be used for determining when to transfuse during the study. The baseline pre-transfusion hemoglobin threshold will be the mean of all documented pre-transfusion hemoglobin values during the 12 weeks prior to C1D1. During treatment, if the pre-transfusion hemoglobin value is increased by \geq 1 g/dL compared to the baseline pre-transfusion hemoglobin threshold for that patient, transfusion should be delayed by a minimum of 7 days and/or the number of units transfused should be reduced by 1 or more RBC units. Patients may be transfused at the investigator's discretion for symptoms related to anemia or other requirements (e.g., infection).

Cohort ^a	ACE-536 Dose Level ^b (mg/kg)	Number of Patients
1	0.2	3-6
2	0.4	3-6
3	0.6	3-6
4	0.8	3-6
5	1.0	3-6
6	1.25	3-6
7	1.5	3-6
Expansion	TBD	30 ^c
Planned Total (All Cohorts):		Approximately 51-72

^a Cohort escalation is based on SRT review and recommendation to enroll additional cohorts and/or the expansion cohort.

^b The ACE-536 dose level for cohort 1 is 0.2 mg/kg. The dose level indicated in the table for all subsequent cohorts is the maximum dose level that can be recommended by the SRT for escalation per the modified Fibonacci dose escalation scheme.

^c The expansion cohort will consist of 30 patients, including a minimum of 12 patients who are non-transfusion dependent and a minimum of 12 patients who are transfusion dependent (including a minimum of 6 thalassemia major patients with onset of regular transfusions before age 4 years, and a minimum of 6 patients with onset of regular transfusions after age 4 years).

9.2. Discussion of Study Design

The primary efficacy endpoint, evaluating sustained increase in hemoglobin during treatment with ACE-536, addresses the primary deficiency in β-thalassemia, namely profound anemia particularly marked in thalassemia major, but clearly present also in thalassemia intermedia and largely driving the clinical picture. A therapy capable of maintaining or increasing hemoglobin levels with chronic treatment can reverse the symptoms associated with anemia, reduce transfusion requirement, decrease iron overload, and decrease the need for iron chelation and the associated adverse effects of chelation treatment. ACE-536 treatment may prove effective in promoting erythroid maturation and reducing ineffective erythropoiesis. It may have additional salutary effects on iron metabolism and bone defects. It is unknown if ACE-536 will also affect the globin chain imbalance characteristic of the disease. Thus, the secondary endpoints were selected to evaluate the impact of ACE-536 on hematology, erythropoiesis, iron metabolism, and bone metabolism parameters.

The initial dose level of 0.2 mg/kg is less than the maximum dose administered in the phase 1 study A536-02 of 0.25 mg/kg, which was safe and well-tolerated, and produced a hemoglobin response in healthy volunteers. The safety measurements in this study are standard for studies with investigational medications. An open-label study, conducted in a limited number of patients, with protocol-specified definitions of dose-limiting toxicity, and with protocol-specified procedures for dose escalation and reduction is considered appropriate for a proof-of-concept study in this target patient population. Dose escalation in sequential cohorts is designed to minimize the risk of adverse events as well as excessive erythroid response and hypertension that may result from a robust response to high drug levels. Individualization of dose level in the expansion cohort, using dose titration rules based on hemoglobin response and dose reduction

rules based on safety information will maximize the proportion of patients having an erythroid response while maintaining safety.

9.3. Selection of Study Population

9.3.1. Inclusion Criteria

Eligible patients must meet **all** of the following criteria:

1. Men or women \geq 18 years of age.
2. For the dose escalation phase of the study: documented diagnosis of β -thalassemia intermedia (transfusion dependent patients must not have begun regular transfusions at age < 4.0 years)
For the expansion cohort: documented diagnosis of β -thalassemia (including β -thalassemia major or β -thalassemia intermedia).
3. Prior splenectomy or spleen size < 18 cm in the longest diameter by abdominal ultrasound (dose escalation cohorts only).
4. Anemia, defined as:
 - a. Mean hemoglobin concentration < 10.0 g/dL of 2 measurements (one performed within one day prior to Cycle 1 Day 1 and the other performed during the screening period [Day -28 to Day -1]) in non-transfusion dependent patients, defined as having received < 4 units of RBCs within 8 weeks prior to Cycle 1 Day 1, OR
 - b. Transfusion dependent, defined as requiring ≥ 4 units of RBCs every 8 weeks (confirmed over 6 months prior to Cycle 1 Day 1).
5. Aspartate aminotransferase (AST) or alanine aminotransferase (ALT) $< 3 \times$ upper limit of normal (ULN).
6. Serum creatinine $\leq 1.5 \times$ ULN.
7. Females of child bearing potential (defined as sexually mature women who have not undergone hysterectomy or bilateral oophorectomy, or are not naturally postmenopausal ≥ 24 consecutive months) must have negative urine or blood pregnancy test prior to enrollment and use adequate birth control methods (abstinence, oral contraceptives, barrier method with spermicide, or surgical sterilization) during study participation and for 12 weeks following the last dose of ACE-536. Males must agree to use a latex condom during any sexual contact with females of child-bearing potential during study participation and for 12 weeks following the last dose of ACE-536, even if he has undergone a successful vasectomy. Patients must be counseled concerning measures to be used to prevent pregnancy and potential toxicities prior to the first dose of ACE-536.
8. Patients are able to adhere to the study visit schedule, understand and comply with all protocol requirements.
9. Understand and able to provide written informed consent.

9.3.2. Exclusion Criteria

Eligible patients must not meet **any** of the following criteria:

1. Any clinically significant pulmonary (including pulmonary hypertension), cardiovascular, endocrine, neurologic, hepatic, gastrointestinal, infectious, immunological (including clinically significant allo- or auto-immunization), or genitourinary disease considered by the investigator as not adequately controlled prior to Cycle 1 Day 1.
2. Folate deficiency.
3. Symptomatic splenomegaly.
4. Known positive for human immunodeficiency virus (HIV), active infectious hepatitis B (HBV), or active infectious hepatitis C (HCV).
5. Known history of thromboembolic events \geq grade 3 according to the National Cancer Institute-Common Terminology Criteria for Adverse Events (NCI-CTCAE) v.4.0 (current active minor version).
6. Ejection fraction $<$ 50% by echocardiogram, MUGA or cardiac MRI.
7. Uncontrolled hypertension defined as systolic blood pressure (BP) \geq 150 mm Hg or diastolic BP \geq 95 mm Hg.
8. Heart failure class 3 or higher (New York Heart Association, NYHA, [Appendix 1](#)).
9. QTc $>$ 450 msec on screening ECG.
10. Platelet count $<$ 100 $\times 10^9$ /L or $>$ 1,000 $\times 10^9$ /L.
11. Proteinuria \geq Grade 2.
12. Any active infection requiring parenteral antibiotic therapy within 28 days prior to Cycle 1 Day 1 or oral antibiotics within 14 days of Cycle 1 Day 1.
13. Treatment with another investigational drug or device, or approved therapy for investigational use \leq 28 days prior to Cycle 1 Day 1, or if the half-life of the previous investigational product is known, within 5 times the half-life prior to Cycle 1 Day 1, whichever is longer.
14. Transfusion event within 7 days prior to Cycle 1 Day 1.
15. Patients receiving or planning to receive hydroxyurea treatment. Patients must not have had hydroxyurea within 90 days of Cycle 1 Day 1.
16. Splenectomy within 56 days prior to Cycle 1 Day 1.
17. Major surgery (except splenectomy) within 28 days prior to Cycle 1 Day 1. Patients must have completely recovered from any previous surgery prior to Cycle 1 Day 1.
18. Iron chelation therapy initiated within 56 days prior to Cycle 1 Day 1.
19. Cytotoxic agents, systemic corticosteroids, immunosuppressants, or anticoagulant therapy such as warfarin or heparin within 28 days prior to Cycle 1 Day 1 (prophylactic aspirin up to 100 mg/day is permitted).

20. Pregnant or lactating females.
21. History of severe allergic or anaphylactic reactions or hypersensitivity to recombinant proteins or excipients in the investigational drug.
22. Prior treatment with sotatercept (ACE-011) or ACE-536.

9.4. Patient Treatment Discontinuation and Withdrawal Criteria

Patients will be informed that they have the right to withdraw from the study at any time for any reason without prejudice to their medical care.

A patient may be discontinued from treatment for any of the following reasons:

- Patient's request
- Patient's unwillingness or inability to comply with the protocol
- Pregnancy
- Use of prohibited medication (e.g., hydroxyurea)
- Medical reason or adverse event, at the discretion of the investigator and/or the medical monitor
- Hypersensitivity reaction to study drug
- At the discretion of the sponsor (e.g., termination of the study or a dose level)

A patient may be withdrawn from the study for any of the following reasons:

- Patient's request
- Patient's unwillingness or inability to comply with the protocol
- Death
- Loss to follow-up
- At the discretion of the sponsor (e.g., termination of the study)

The reasons for study withdrawal and treatment discontinuation must be recorded in the patient's CRF. The investigator must notify the sponsor, the medical monitor and the contract research organization (CRO) immediately when a patient has been discontinued/withdrawn due to an AE. Patients who discontinue treatment early should complete the end of treatment (EOT) follow-up visit at the time of discontinuation and then complete the end of study (EOS) follow-up visit approximately 28 days later.

The investigator must notify the sponsor and the CRO when a patient has been discontinued/withdrawn for reasons unrelated to the study or study drug (e.g., withdrawn consent, lost to follow up).

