- ¹⁰ **Pregnancy** test (urine or serum) and menstrual history is required prior to C1D1 for female patients of child bearing potential only.
- ¹¹ Transfusion history will be collected for 12 months prior to C1D1.
- ¹² **End of Treatment (EOT):** Should be performed 28 days (\pm 7 days) after the last dose of ACE-536. Patients who discontinue treatment early should complete the end of treatment visit at the time of discontinuation and complete the Day 141 follow up visit 28 days (\pm 7 days) after the EOT visit.
- ¹³ **End of Study (EOS):** Should be performed 28 days (\pm 7 days) after the Day 113/EOT visit (56 days after the last dose of ACE-536).
- ¹⁴ **Day 85 \pm 2 days** is the last possible study day that ACE-536 may be administered, regardless of the cycle.
- ¹⁵ If a **dose delay** is required per the dose modification rules the patient will not be dosed. The patient will return weekly to assess hematology results and adverse events until the patient is eligible to administer the next dose of ACE-536.
- ¹⁶ If the patient has a positive ADA result at their last assessment, the patient may be asked to return approximately every three months for additional testing until a negative result is obtained or the result is considered stabilized.
- ¹⁷ MRI for liver iron content will be performed at selected sites.
- ¹⁸ For the first dose of ACE-536, dosing should occur after a minimum of 7 days post-transfusion; subsequent doses should not be given within 24 hours of transfusion or planned transfusion.
- ¹⁹ Administration of quality of life questionnaires, including but not limited to FACT-An and SF-36 is required for patients in the expansion cohort only.
- ²⁰ QoL questionnaires including but not limited to FACT-An and SF-36 should be completed at the EOT visit only for expansion cohort patients who discontinue treatment early.
- ²¹ Abdominal ultrasound of the spleen is required for patients with no prior splenectomy in the dose escalation cohorts only. Patients in these cohorts with clinical signs of a change in spleen size or abnormality should have an abdominal ultrasound as needed throughout study.
- ²² Pregnancy test is not required at Day 141/EOS.
- ²³ Physical exam should include an optional evaluation of gonadal size in males at C1D1, EOT, and EOS visits only.
- ²⁴ MRI of the chest and abdomen for EMH masses and spleen, DXA for BMD and 6MWT for NTD patients will be performed in the expansion cohort patients only, at selected sites.

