10. TREATMENT OF PATIENTS

10.1. Selection and Timing of Dose for Each Patient

Once a patient is enrolled, the appropriate dose of ACE-536 will be administered as a subcutaneous injection on Cycle 1 Day 1. Subsequent doses will be administered every 3 weeks on Day 1 of the cycle. Study day 85 (\pm 2 days) is the last possible study day that ACE-536 can be administered, regardless of the cycle. Dose reductions may be required for individual patients as outlined in the Patient Dose Modifications Rules ([Section 10.8.1](#)). If a dose delay is required, the patient will return weekly for assessment of hematology results and adverse events until the patient is eligible to receive the next dose of ACE-536. Patients will be asked to return to the clinic for two follow-up visits, occurring approximately 28 days and 56 days after their last dose of ACE-536. If a patient has a positive anti-drug antibody (ADA) result at the last visit, the patient may be asked to return for additional ADA testing every three months, until a negative result is obtained or the result is considered to be stabilized.

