12.4. End of Treatment Visit

- The end of treatment visit should occur approximately 28 days after the last dose of ACE-536.
- Patients who discontinue treatment early should complete the end of treatment visit at the time of discontinuation.
- Patients in the expansion cohort who discontinue treatment early or do not complete the Day 85 visit should complete the quality of life questionnaires at the end of treatment visit.
- An abdominal ultrasound of the spleen will be performed for patients without a history of splenectomy in the dose escalation cohorts only.
- An MRI will be performed at selected sites to evaluate liver iron content (all cohorts), and an MRI of the chest and abdomen for EMH mass size (expansion cohort only), and spleen size (expansion cohort only).
- A DXA will be performed at selected sites to evaluate total body, lumbar spine and total hip BMD (expansion cohort only).
- A 6MWT will be performed in NTD patients at selected sites (expansion cohort only).
- Leg ulcer(s) size will be assessed in patients with leg ulcers; photographs should be taken to document changes.
- Pregnancy test (urine or serum) and menstrual history will be collected for women of child bearing potential.
- Physical exam should include an optional evaluation of gonadal size of male patients.

- For blood pressure measurements, if the systolic blood pressure is ≥ 150 mmHg, the diastolic blood pressure is ≥ 95 mmHg, and/or the absolute increase in either measure from baseline is ≥ 20 mmHg, perform one repeat blood pressure assessment after a minimum of 15 minutes.

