12.5. End of Study Visit

- The end of study visit should occur approximately 28 days after the end of treatment visit.
- Patients who discontinue treatment early should complete the end of study visit approximately 28 days after the end of treatment visit.
- For the expansion cohort patients only, administration of quality of life questionnaires.
- If a patient has a positive anti-drug antibody (ADA) result at the last visit, the patient may be asked to return for additional ADA testing every three months, until a negative result is obtained or the result is considered to be stabilized.
- Menstrual history will be collected for women of child bearing potential; pregnancy test not required.
- Physical exam should include an optional evaluation of gonadal size of male patients.
- For blood pressure measurements, if the systolic blood pressure is ≥ 150 mmHg, the diastolic blood pressure is ≥ 95 mmHg, and/or the absolute increase in either measure from baseline is ≥ 20 mmHg, perform one repeat blood pressure assessment after a minimum of 15 minutes.
- Leg ulcer(s) size will be assessed in patients with leg ulcers; photographs should be taken to document changes.

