14.5. Documentation and Methods of Reporting of Adverse Events by Investigator

It is the responsibility of the Investigator to document all adverse events that occur during the study. Patients will be evaluated and questioned generally for AEs during the course of the study, starting at the signing of the informed consent. The Investigator must report in detail all adverse signs and symptoms which are either volunteered by subjects or observed during or following the course of investigational product administration on the appropriate CRF page. All non-serious AEs occurring after signing of the ICF until a patient is dosed on Cycle 1 Day 1 are to be documented on the medical history CRF. All AEs and SAEs occurring after the Cycle 1 Day 1 dose through 56 days after the last study drug administration (End of Study visit) are to be reported and documented on the AE CRF.

All AEs spontaneously reported by the patient and/or in response to an open question from study personnel or revealed by observation, physical examination, or other diagnostic procedures will be recorded on the AE CRF. Any clinically relevant changes in laboratory assessments, or other clinical findings as described in [Section 14.1](#), are considered AEs and must be recorded on the AE CRF. AEs are to be followed for resolution as described in [Section 14.6](#).

It is important that each AE report include a description of the event, duration (onset and resolution dates), severity, relationship with ACE-536, any other potential causal factors, any treatment given or other action taken (including dose modification or discontinuation of ACE-536) and outcome. In addition, serious AEs (SAEs) should be identified and the

appropriate seriousness criteria documented. AEs categorized as SAEs must also be documented using an SAE Report Form as described in [Section 14.5.1](#).

Specific guidance can be found in the CRF Completion Guidelines provided by the Sponsor or designee.

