14.5.1. Documentation of Serious Adverse Events

All SAEs that occur after the first study drug administration on Cycle 1 Day 1 until 56 days after the last study drug administration (End of Study visit) are to be documented on the AE CRF. SAEs should not be reported for patients who are considered screen failures unless the event is deemed due to a protocol required procedure.

For all SAEs, an SAE form must be completed with as much information as possible and submitted within the time frame described in [Section 14.7](#).

When new significant information is obtained, as well as when the outcome of an event is known, the investigator should record the information on a new SAE form. If the patient was hospitalized, a copy of the discharge summary must be included as part of the patient medical file. In all instances, the investigator should follow up with patients until the outcome of the SAE is known.

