14.6. Reporting Period and Monitoring of Patients with Adverse Events

As described in [Section 14.5](#), all AEs must be recorded in the CRF up until the end of the treatment period. All patients who took at least one dose of study drug, whether they completed the treatment period or not, should complete the end of treatment procedures.

All AEs will be followed until clinical database lock (or resolution if it occurs before database lock). All SAEs will undergo active follow up until resolved or the event becomes chronic or stable. Follow up data for SAEs obtained after clinical database lock will be incorporated into the ACE-536 safety database.

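### Protocol 14.6 ends adverse event recording 28 to 56 days before 14.5 does, and the 56-day point is wrongly labelled as the End of Study visit for early discontinuers

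*Protocol*

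**What the plan says.** **AE reporting period.** Protocol 14.5 requires AEs and SAEs to be recorded from the first dose "through 56 days after the last study drug administration (End of Study visit". Section 14.5.1 uses the same limit for SAEs: "until 56 days after the last study drug administration (End of Study visit". SAP 5.8.2 also uses 56 days after the last dose and treats every AE collected as treatment-emergent. Protocol 14.6 opens by referring to 14.5 and then says "all AEs must be recorded in the CRF up until the end of the treatment period".

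**Follow-up visits in general.** Protocol 10.1 describes two follow-up visits "occurring approximately 28 days and 56 days after their last dose". Footnote 13 of the Schedule of Events puts End of Study (EOS) 28 days (±7) after End of Treatment (EOT) and glosses this as "56 days after the last dose of ACE-536". SAP 5.1 repeats that gloss.

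**Follow-up visits after early discontinuation.** Protocol 12.4: "Patients who discontinue treatment early should complete the end of treatment visit at the time of discontinuation". Protocol 12.5: "Patients who discontinue treatment early should complete the end of study visit approximately 28 days after the end of treatment visit". Section 9.4 says the same ("complete the end of study (EOS) follow-up visit approximately 28 days later"), and footnote 12 and SAP 3.2 agree.

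**The concern.** Section 14.6 is the section a site would open to learn when AE recording stops, and its answer differs from the section it cites. A site that follows it literally would stop recording non-serious AEs during follow-up, while SAP 5.8.2 tabulates AEs as though collection had run to 56 days. Incidence would then be understated, and no table would show it.

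The second fault is narrower. Four places tie the 56-day limit to the EOS visit, but for a patient who stops early that visit usually comes sooner. A site could close AE collection at the visit or at day 56, and the label does not say which governs.

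**Working it through.** **Inputs.** Dosing is every 3 weeks, with the last possible dose on Day 85 (±2) (Protocol 10.1). EOT is 28 days (±7) after the last dose and EOS 28 days (±7) after EOT (footnotes 12 and 13). The synopsis gives a 12-week treatment period and an 8-week follow-up period. For early discontinuers, EOT is on the day of stopping and EOS 28 days later.

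**Step 1: the plan's own figure, for a completer.** EOT = 85 + 28 = Day 113. EOS = 113 + 28 = Day 141. 141 − 85 = 56 days, so the 56-day label is right for completers.

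**Step 2: 14.6 against 14.5, for a completer.** The documents give no day on which the treatment period ends. Shortfall = 141 − end day.

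| Reading of the end of the treatment period | End day | Shortfall (days) |
|---|---|---|
| 12 weeks, to the Day 85 dose | 85 | 56 |
| Last cycle 5 visit (C5D15) | 99 | 42 |
| EOT visit | 113 | 28 |

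No reading reaches Day 141.

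**Step 3: 14.6 against 14.5, for an early discontinuer.** Let d be the days from last dose to stopping. If the treatment period closes at EOT, which is the day of stopping, the shortfall is 56 − d: 56 days at d = 0 and 35 at d = 21.

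**Step 4: EOS for an early discontinuer.** EOS after last dose = d + 28. Nominal gap to 56 = 56 − (d + 28) = 28 − d.

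| d | EOS, days after last dose | With the ±7-day window | Nominal gap to 56 |
|---|---|---|---|
| 0 | 28 | 21-35 | 28 |
| 7 | 35 | 28-42 | 21 |
| 14 | 42 | 35-49 | 14 |
| 21 | 49 | 42-56 | 7 |
| 28 | 56 | 49-63 | 0 |

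The range d = 0 to 21 is inferred from the 3-week cycle.

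**Step 5: how exact 56 days is for completers.** With both windows, EOS can fall between (28 − 7) + (28 − 7) = 42 and (28 + 7) + (28 + 7) = 70 days after the last dose. A nominal EOS for an early discontinuer at d = 14 to 21 (42 to 49 days) lies inside that range.

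**The case against.** **On 14.6.** Its opening reference to 14.5 suggests that 14.5 controls, and SAP 5.8.2 confirms 56 days. A careful site would probably resolve the conflict that way. That supports calling it a one-phrase correction. It does not make the sentence right, because 14.6 is an operative instruction under a heading about the reporting period.

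**On the early-discontinuation schedule.** The rule is explicit and repeated in 9.4, 12.4, 12.5, footnote 12 and SAP 3.2. Footnote 12 stands directly above footnote 13, and a specific rule governs a general one. Section 10.1 says only approximately. The largest gap needs a stop on the dosing day itself. Dose-modification rules are assessed before dosing, and held doses bring weekly visits, so many stops would fall near d = 21 or later, where the gap is 7 days or less. All of this stands: the schedule is a design choice, and only the unqualified label is at fault.

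**Stronger readings a reader might infer.**

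- *AEs of early discontinuers go unreported after EOS.* The documents do not support this. The duty in 14.5 and 14.5.1 is counted from the last dose, and 14.6 follows AEs to resolution or database lock and SAEs until resolved, chronic or stable. What is missing is a scheduled visit in the final 7 to 28 days (nominal, d = 0 to 21).
- *EOS must therefore move to day 56.* That is debatable. It adds follow-up time, and under SAP 3.3 patients who do not roll over directly must wait at least 28 days after EOS, so a later EOS would delay extension entry.
- *The primary efficacy result is biased.* Transfusion-dependent patients who stop early may have fewer rolling 12-week windows. But SAP 5.7.1 states where the search ends, and all efficacy is analysed by ITT, the Efficacy Evaluable population having been removed (SAP 5.13). Under ITT, fewer windows can only lower the response rate. The number of patients affected is not given.

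**Conclusion.** Section 14.6 is wrong as written. It contradicts 14.5, 14.5.1 and SAP 5.8.2 for all patients, by 28 to 56 days in a completer depending on how the end of the treatment period is read. These figures assume the last dose on Day 85 and nominal visit days.

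The 56-day EOS label in 14.5, 14.5.1, footnote 13 and SAP 5.1 is right for completers and inexact for early discontinuers, whose EOS falls nominally 28 to 49 days after the last dose for stops at d = 0 to 21. The visit window can close the gap at d = 21, and nominally it is gone at d = 28. This part calls for clarification only. The documents do not show how many patients stopped early, or which end date sites applied.

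**What to change.** 1. In Protocol 14.6, replace the end of the treatment period with 56 days after the last dose of ACE-536.
2. In Protocol 14.5 and 14.5.1, schedule footnote 13 and SAP 5.1, limit the equation of 56 days with EOS to patients who complete treatment. State that AE and SAE collection runs to 56 days after the last dose even when EOS comes earlier.
3. Optionally, add a line to the SAP reporting actual days of follow-up after the last dose for early discontinuers. SAP 5.3 and 5.5 now plan only disposition and exposure.

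The EOS schedule stays as it is. The cost is a few phrases and at most one extra summary, with no added visits. The SAP is dated August 2017 and describes enrolment and dosing in the past tense. If visits are already complete, rewording the protocol cannot change what was collected, and item 3 is the part that still helps.
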